7.4.6 Receiving, Storage, Dispensing and Return

7.4.6.1 Receipt of Test Article

The study drug (liraglutide or placebo) will be obtained from Synergy pharmacy after the subject is enrolled into the study. After enrollment, study team members will inform Synergy Pharmacy and will provide the information about study subjects required for dispensing the study drug.

Novo Nordisk will supply the clinical variant of Saxenda® (Comparator) and placebo in a pre-filled, multi-dose pen that delivers doses of 0.6 mg, 1.2 mg, 1.8 mg, 2.4 mg, or 3 mg of liraglutide as a subcutaneous injection. Each 1 ml of Saxenda solution contains 6 mg of liraglutide; each pre-filled pen contains a 3 ml solution of Saxenda equivalent to 18 mg of liraglutide.

Upon receipt of study shipments from Synergy, a Caron pharmacy technician will inventory/check the shipment using the shipping invoice to record lot number, expiration date, breakage, storage condition, and total quantities. The shipping invoice will be signed and dated. The shipment will

be refrigerated during shipment, and recorded on the study drug accountability log. The shipping invoice will be filed in the shipping file and the study medication will be placed into appropriate storage conditions.

7.4.6.2 Storage

The storage of the medication will be at the medical detox unit at the CaronTC. In this unit is a locked room (nurses' clinic) that contains a locked refrigerator where the medication will be stored. Therefore, the medication will be double locked. Only Caron nurses will have access to the medication. The study drugs will be refrigerated at 2°C to 8°C during storage. Caron nurses will check and record temperature daily.

7.4.6.3 Preparation and Dispensing

Synergy Pharmacy will prepare and deliver the medication after receiving a scanned signed informed consent from Caron. Synergy Pharmacy will use the randomization log to prepare the study medications for each participant. The study medications will be pre-filled injectable pens that are identically labeled for double blinding. Dispensed study medications will be labeled with the label from the Synergy Pharmacy's Computer System, conforming to state and federal law. The study's required labeling will be attached to the dispensed product in addition to the pharmacy label. No parts of the study's label will be obliterated by the pharmacy label. All study medications will be labeled with the caution, "New Drug- Limited by Federal (or United States) law to investigational use."

The study drug (liraglutide or placebo) will be ordered by the medical staff at Caron, stored in the medical unit, and dispensed using the supplied, prefilled, multi-dose pens that deliver doses of 0.6 mg, 1.2 mg, 1.8 mg, 2.4 mg, or 3 mg of liraglutide as a subcutaneous injection. Study staff will maintain medication logs including information on time of administration, batch number, and expiration date. Study drugs will not be used after the expiration or use-by date.

Study treatment injection pens (liraglutide or placebo) will look identical.

The study drug will be obtained from the study nurse and self-administered by the participant under the observation of the study staff or study nurse.

7.4.6.4 Return or Destruction of the Test Article

Once the study drug is prepared for the subject, it can only be administered to that subject. Final reconciliation of the medication will take place at the CaronTC, if appropriate. The CaronTC performs these procedures according to DEA regulations. Non-controlled substances are stored in locked medical bins, which are then shipped to a company that will safely destroy the medication. Patients who do not complete the entire study will have their medication destroyed via Caron's established medication disposal protocols.

7.4.6.5 Prior and Concomitant Therapy

A concomitant therapy is any medication which is administered between study enrollment and the end of the study drug treatment phase. All concomitant therapies will be monitored daily and recorded at minimum

once weekly by study team members during the duration of the treatment phase with the study drug.

The subjects recruited will be current patients in a residential facility for the treatment of opioid dependence. Since the physicians at Caron will be approving patient eligibility, they will know current and past patient medication regimes. Subjects may be taking concomitant medicines/therapies for various reasons at the treatment center. The pharmacy staff at Caron will also know which medications may not be permitted to take with the medication during the study, due to potential counteracting affects.

Precautions: Saxenda is contraindicated with the use of insulin or any other GLP-1R agonist; the use of these medications are identified in the exclusion criteria.

Respiration and heart rate will be monitored at baseline and following all dosage increases.

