In preclinical studies, treatment with the GLP-1R agonist, Exendin-4 (Ex-4), has been shown to reduce a conditioned place preference for, and the accumbens dopamine response to, nicotine, cocaine, and amphetamine, and reduces cocaine self-administration in rats [15, 16, 20, 21]. Likewise, treatment with Ex-4, in a dose that does not affect responding for sucrose, decreases fixed and progressive ratio responding for cocaine [18] and, when administered centrally, cocaine-induced reinstatement [22]. Finally, the use of a GLP-1R agonist increases insulin secretion, while inhibiting glucagon, only in response to increases in glucose levels [23, 24]. As such, this treatment can potentially be used in patients with OUD without diabetes without the risk of hypoglycemia. Substantial evidence from randomized controlled trials indicate that the use of a GLP-1R agonist can produce significant, sustained weight loss in obese but non-diabetic people without causing any adverse effects on circulating glucose blood pressure, HbA1c or their lipid profile [25-27], suggesting it could be used safely in OUD patients. GLP-1R agonists, then, are promising for the treatment of substance use disorder (SUD) in humans. Further, the intervention can be readily translated for a new indication, as various formulations of GLP-1R agonists are approved for treatment of obesity and Type 2 Diabetes Mellitus (T2DM) in humans [21, 28] and already are in clinical trials for nicotine and alcohol use disorders [29-34].

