3.2 Exclusion Criteria

Patients will be excluded from study entry if any of the following exclusion criteria exist at screening:

- 1. Age < 18 or > 75 years
- 2. Women who are pregnant, planning pregnancy, breastfeeding, or unwilling to use adequate contraceptive measures
- 3. History of angioedema, serious hypersensitivity reaction, or anaphylactic reaction to liraglutide or another glucagon-like peptide-1 receptor (GLP1R) agonist
- 4. Personal or family history of medullary thyroid carcinoma (MTC) or patients with multiple endocrine neoplasia syndrome type 2 (MEN 2) or thyroid nodule
- 5. Type I diabetes or history of diabetic ketoacidosis
- 6. Type II diabetes mellitus
- 7. Hypoglycemia on intake visit (blood glucose < 70 mg/dL)
- 8. End-stated renal failure on dialysis **or** glomerular filtration rate (GFR) <30mL/min per 1.73 square meters **or** previous renal transplant
- 9. Severe hepatic impairment (AST or ALT levels > 3 times upper limit of normal range) or previous liver transplant
- 10. Current or past diagnosis of pancreatitis, gastroparesis, or other severe gastrointestinal disease
- 11. Current or past diagnosis of gallbladder disease or gallstones
- 12. Serious cardiovascular disease within the past 6 months (e.g. uncontrolled hypertension, heart failure, significant cardiac arrhythmias, myocardial infarction, presence of angina pectoris, symptomatic coronary artery disease, deep vein thrombosis, pulmonary embolism, second- or third-degree heart block, mitral valve or aortic stenosis, hypertrophic cardiomyopathy, stroke)

- 13. Severe co-occurring psychiatric disorder (e.g., bipolar disorder, psychotic disorder, schizophrenia) that would, in the opinion of the Principle Investigator or study physician, interfere with participating in the study, such as if the patient needs a higher or different level of care and is going to be transferred out of Caron.
- 14. Suicidal ideation within the past 1 month, or history of suicide attempts within the past 1 year, unless participation is cleared by clinician assessment and/or judgement.
- 15. Treatment with any investigational drug in the one-month preceding the study
- 16. Previous randomization for participation in this trial
- 17. Abnormal physical exam findings, vital signs (blood pressure, heart rate, respiratory rate, body temperature), EKG measurements, and safety lab values that are deemed clinically significant by study physician

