4.0 Recruitment Methods

4.1 Identification of subjects

Patients who plan to remain in residential treatment for a minimum of 4 weeks at CaronTC will be identified. Patient records will be evaluated by Caron-based study staff against the study inclusion and exclusion criteria.

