4.2 Recruitment process

4.2.1 How potential subjects will be recruited.

All eligible patients will be approached and recruited in the same manner following the study protocol procedures. Only IRB-approved study team members (Physicians or staff) at CaronTC will first interact with the patient in a consultation session. During the initial consultation session, the physician/staff will briefly explain the proposed study and ask the patient if they would be interested in discussing further with a research study member. If the patient is interested, a trained research study team member will discuss the full study including any risks and benefits associated with participation.

4.2.2 Where potential subjects will be recruited.

Potential subjects will be recruited on the Professionals Unit at CaronTC. Subjects may also be drawn from other units at the CaronTC if there is a planned stay of a minimum of 4 weeks.

4.2.3 When potential subjects will be recruited.

Potential subjects will be recruited prior to any study procedures taking place.

4.2.4 Describe the eligibility screening process and indicate whether the screening process will occur before or after obtaining informed consent. Screening begins when the investigator obtains information about or from a prospective participant in order to determine their eligibility. In some studies, these procedures may not take place unless HIPAA Authorization is obtained OR a waiver of HIPAA Authorization when applicable for the screening procedures is approved by the IRB.

Screening of subjects at admission is expected prior to obtaining consent to confirm that they have an established diagnosis of OUD.

Once informed consent is obtained, patients will undergo additional screening to determine if they are eligible to participate in the study based on the inclusion/exclusion criteria

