7.4 Test Article(s) (Study Drug(s) and/or Study Device(s))

7.4.1 Description

Liraglutide (Saxenda®, Novo Nordisk) is a glucagon-like peptide-1 (GLP-1) receptor agonist approved by the FDA for the treatment of T2DM (1.8 mg/day) and obesity (3.0 mg/day) and has been deemed safe for use in populations with a history of substance use disorder (American Association of Clinical Endocrinologists, 2016; see also Saxenda package insert, Plainsboro, NJ: Novo Nordisk A/S; 2015).

Liraglutide 6 mg/ml (Novo Nordisk), will be provided as a solution in a pre-filled, multi-dose pen that delivers doses of 0.6 mg, 1.2 mg, 1.8 mg, 2.4 mg, or 3 mg of liraglutide as a subcutaneous injection.

Liraglutide and placebo will be delivered as a solution (liquid) in identical multidose pens. In order to use Saxenda® as a blinded comparator in the clinical trial, the presentation has been modified from the Marketed product. For Saxenda® (Comparator) the primary packaging materials are identical to what is approved in the Marketing authorization, except that the cartridge for the comparator is produced with an army green closure cap. The closure cap in the currently marketed Saxenda® product is a light blue cap. The cap is not in contact with the product and has no impact on the stability of the comparator. For Saxenda® (Comparator) the pen is identical to what is approved in the Marketing Authorization, except for the color of the cartridge holder and the pushbutton, where the Marketed version is purple and the clinical comparator is light brown. The pen is not in contact with the product and its color has no impact on the stability of the comparator.

New, unused liraglutide/vehicle pens will be stored according to the information stated on the trial product label. Pens will be disposed of after 30 days of initial use.

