7.4.2 Treatment Regimen

The recommended maximum dosage is 3 mg/day, administered any time of day. This choice in dosage is based on the current FDA-approved dosing regimen for liraglutide to help patients manage craving in obesity. The initial dose will start at 0.6 mg/day for the first 6 days, then titrate by 0.6 mg every 6 days — to reduce the likelihood of adverse gastrointestinal symptoms — until 1.8 mg/day is reached for the 3-dose intervention and 3 mg/day is reached for the 5-dose intervention. Participants will be taught self-administration by study/nursing staff. All self-administrations will occur via blinded, multi-dose subcutaneous injection pens, and will be observed by nursing staff at CaronTC.

Participants will receive medications daily at a specified time (prior to breakfast) throughout the study. Participants will be taught to inject the solutions subcutaneously in the abdomen, thigh, or upper arm, and will administer daily injections under the supervision of a study nurse or staff member. Participants will be taught by study staff nurses to attach the needle, check the drug/vehicle flow, select the dose, inject the dose, remove the needle, and dispose of the needle. Participants will always use a new needle for each dose administration in the study. Dosages will be chosen based on current titration level in the study.

There is no provision to provide study treatment after the study.

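### Section 7.4.6.5 says use of insulin or another GLP-1R agonist is an exclusion, but no criterion in 3.2 lists it, so a non-diabetic user of a marketed GLP-1R agonist passes the written screen

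*Combined protocol and SAP*

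**What the plan says.** Section 7.4.6.5 (Prior and Concomitant Therapy) gives one precaution on drug combinations: "Saxenda is contraindicated with the use of insulin or any other GLP-1R agonist; the use of these medications are identified in the exclusion criteria".

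The exclusion criteria are in section 3.2, numbered 1 to 17 without a gap. Two of them come near the subject. Criterion 3 names the drug class: "History of angioedema, serious hypersensitivity reaction, or anaphylactic reaction to liraglutide or another glucagon-like peptide-1 receptor (GLP1R) agonist". Criterion 15 concerns recent treatment: "Treatment with any investigational drug in the one-month preceding the study".

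Screening is tied to these lists at two points. Section 4.1 says "Patient records will be evaluated by Caron-based study staff against the study inclusion and exclusion criteria", and section 4.2.4 says that after consent "patients will undergo additional screening to determine if they are eligible to participate in the study based on the inclusion/exclusion criteria".

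On who might already be taking such a drug, section 2.1 says "various formulations of GLP-1R agonists are approved for treatment of obesity and Type 2 Diabetes Mellitus (T2DM) in humans". Section 7.4.1 describes liraglutide as "approved by the FDA for the treatment of T2DM (1.8 mg/day) and obesity (3.0 mg/day", and section 7.4.2 states: "The recommended maximum dosage is 3 mg/day, administered any time of day".

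**The concern.** A reader of 7.4.6.5 is told that the exclusion list already keeps out anyone on a contraindicated drug. If the list does not do so, staff who screen faithfully against it can pass a patient whom the protocol itself says should not receive the study drug. At stake is the safety of a small number of patients who could receive two agents of the same class, and the internal consistency of the eligibility rules. The intent to exclude is plain from 7.4.6.5. The question is whether the operative list carries that intent.

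**Working it through.** The plan gives no figure on this point, so the check is mainly a comparison of texts, followed by a short dose illustration.

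**Step 1. Does any criterion in 3.2 list use of insulin or a GLP-1R agonist?**

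- Criterion 3 names GLP-1R agonists, but only for a past allergic-type reaction. A patient who tolerates the drug is not caught.
- Criteria 5 and 6 exclude type I and type II diabetes. They reach drug use only through the diagnosis.
- Criterion 15 covers investigational drugs. A marketed product is outside it.
- Criterion 17 covers clinically significant findings on examination, vital signs, EKG and laboratory tests. It says nothing about medication.
- The other criteria concern age, pregnancy, other diagnoses, suicidality and previous randomization.

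Result: 0 of 17 list use of insulin, and 0 of 17 list use of another GLP-1R agonist.

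**Step 2. Who is left uncovered?**

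- Insulin users: removed by criteria 5 and 6, apart from rare forms of diabetes that are neither type I nor type II.
- GLP-1R agonist users treated for type II diabetes: removed by criterion 6.
- GLP-1R agonist users without diabetes: removed by nothing. Section 2.1 says the class is approved for obesity, and sections 3.1 and 3.2 set no weight or BMI limit, so the protocol's own text makes this patient possible.

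**Step 3. Does the omission reach screening?** Yes. The record review in 4.1 and the post-consent screening in 4.2.4 are both made against the written criteria.

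**Step 4. Is it repaired later?** Not in writing. The withdrawal rule in 3.3.1, repeated in 18.7, removes participants who develop a new condition from the exclusion criteria. Starting a drug that the criteria do not list triggers nothing.

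**Step 5. Dose illustration.** Inputs:

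- patient's own liraglutide dose 3.0 mg/day, the obesity dose in 7.4.1 (assumption: the drug is liraglutide and it is continued);
- study dose 1.8 mg/day, the top step of the 3-dose procedure in which everyone is enrolled (7.1), or 3.0 mg/day, the top step for 5-dose participants only;
- maximum 3 mg/day (7.4.2).

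Total = own dose + study dose; multiple = total / 3.0.

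- At the 1.8 mg step: 3.0 + 1.8 = 4.8 mg/day; 4.8 / 3.0 = 1.6.
- At the 3.0 mg step: 3.0 + 3.0 = 6.0 mg/day; 6.0 / 3.0 = 2.0.

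This applies only to a patient allocated to liraglutide. With 1:1 randomization, that is an expected half of any such patients. How many there would be cannot be estimated from the documents.

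**The case against.** The strongest reply is that the rule is already in the protocol. Section 7.4.6.5 states the contraindication and says such users are meant to be excluded. The same section says that site physicians approve eligibility knowing current and past medication, that pharmacy staff will know which drugs are not permitted, and that concomitant therapies are monitored daily. Current medications are also taken from the medical record at enrolment (7.2.1). The list in 3.2 is therefore not the only barrier.

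Most of this stands, and it is why the point is minor. It does not remove the inconsistency. The safeguards provide information and judgement but no written decision rule: no list of prohibited drugs is given, and the one sentence that could serve as the rule sends the reader to a criterion that does not exist.

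Two further inferences should be resisted. A reader might conclude that a washout period is also missing. Section 7.4.6.5 speaks of concurrent use, and the documents give human half-lives only for exenatide (2.4 h) and liraglutide (13 h), both in 2.2, so they do not settle whether a washout is needed or how long it should be. A reader might also start the dose illustration from 1.8 mg/day. Section 7.4.1 ties that dose to type II diabetes, which criterion 6 excludes, so 3.0 mg/day is the approved dose relevant to the patient in question.

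**Conclusion.** The cross-reference in 7.4.6.5 is wrong as written, and the list used for screening does not carry the exclusion that the protocol intends. The practical gap is narrow: a non-diabetic patient on a marketed GLP-1R agonist. Severity is minor: an internal inconsistency with a small safety consequence.

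The dose figures rest on three assumptions: the patient's drug is liraglutide at the full obesity dose, it is continued despite the safeguards, and the patient is allocated to the active arm. Even then, section 10.0 describes overdose as severe nausea and vomiting with occasional abdominal pain and diarrhea, and says that no reported case led to hypoglycemia. A reader who infers a major hazard goes further than the documents do.

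Nor do the documents support reading this as a threat to the comparison of arms. They give no prevalence of GLP-1R agonist use in this population, and no effect on the treatment contrast, in either direction, can be derived from them. Sample size, power and significance level are untouched.

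**What to change.** Add one criterion to section 3.2: *Current use of insulin or any GLP-1R agonist.* That makes the sentence in 7.4.6.5 true. Leave any washout period to the sponsor, who can check the longer-acting agents. In 3.3.1 and 18.7, state that starting such a drug during treatment is a reason to stop study drug.

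No new procedure is needed, because current medications are already collected (7.2.1). The costs are the loss of a few otherwise eligible patients and a protocol amendment, which under section 18.5 must be approved by the IRB and NIDA before it takes effect. Given the low urgency, the change could be included in the next planned amendment.

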8.0 Subject Numbers and Statistical Plan

8.1 Number of Subjects

This study will enroll 50 opioid use disordered patients in residential treatment.

8.2 Sample size determination

This is an exploratory study to accumulate pilot data. The primary endpoint of this study is cue-elicited self-reported craving VAS scores. A sample size of N=20 per group will give 80% power to detect an effect size of 0.91 based on a two-sided two-sample t-test with a significance level of alpha=0.05. Accounting for an estimated 20% attrition rate, we plan to randomize a total of 20*2/0.8=50 patients in the study. To preserve statistical power, the sample will not be balanced with regard to MAT and non-MAT participants.

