7.4.3 Method for Assigning Subject to Treatment Groups

Participants will receive either liraglutide or placebo in a two-arm parallel group study. Interventions will be randomized in a 1:1 ratio using permuted-block randomization algorithm. The randomization will be performed using a random number generator via the PLAN procedure within SAS software, version 9.4 (SAS Institute Inc., Cary, NC). Personnel in the Department of Public Health Sciences (PHS) will use the PLAN procedure within SAS software to generate a randomization list using variable-size, random permuted blocks to ensure that the number of participants in each arm is balanced after each set of B randomized participants, where B is the block size. Personnel in PHS will choose the block sizes without revealing it to any of the investigators or study personnel who will be collecting and reviewing outcomes data. The randomization sequence will be uploaded to a secure REDCap database. Synergy Pharmacy will be given access to this REDCap database to provide the blinded, randomized labeling prior to shipping the study drugs to the CaronTC

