8.3 Statistical methods

The primary aim is to test whether liraglutide reduces craving in patients recovering from OUD in residential treatment. Analysis of covariance (ANCOVA) will be used to compare liraglutide versus placebo treatment groups controlling for baseline values of craving. Linear mixed effects models for repeated measurements will also be used to evaluate the difference in changes in these primary outcomes between treatment groups. The baseline and post-treatment outcomes are treated as dependent variables in the mixed model. Subjects with missing values can be incorporated in the mixed model analysis when data are missing at random. The moderating effect will be assessed by adding the interaction term between moderator and treatment group in the models.

SAS (version 9.4) and R (version 3.2.5) software will be used for analyses with a significance level of 0.05. Summary statistics including means, medians, ranges, and standard deviations will be computed for each continuous variable and frequencies with percentages for categorical variables. Identified data outliers will be further examined to determine if they are data entry errors, in which case they will be modified when possible; otherwise, values will be kept for final analysis.

Primary outcomes to assess efficacy are: (1) cue-elicited drug craving rated on a 100-pt VAS; and (2) ambient drug craving, derived from EMA of daily craving throughout the study period. Data analyses for cue-elicited craving will consist of a 2×2 ANOVA with medication status (pre- vs post-medication) as a within-group variable and medication type (liraglutide vs placebo) as a between-group variable.

Secondary analyses of self-reported craving measures will evaluate the role of MAT, specifically BUP/NA, in these results.

EMA and Wearable Assessment: Ambient drug craving derived from the EMA will be analyzed as a multilevel model in the regression framework and will test effects of medication status within-person and medication type between-person. Secondary analyses of EMA will examine the effect of time (e.g. study day) to identify differences across condition in the rate of decline in craving across time.

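### MAT status at randomisation is collected but appears in neither the allocation scheme nor any primary craving model; adding it is a nearly free improvement

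*Combined protocol and SAP*

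**What the plan says.** Section 2.2 describes a mixed population: residential patients on counselling alone, or on counselling plus buprenorphine/naloxone. Section 7.1 states that enrolment does not hold up standard OUD therapy, including that drug. Section 7.2.1 takes current medication from the medical record at enrolment.

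- **Allocation (7.4.3).** "Interventions will be randomized in a 1:1 ratio using permuted-block randomization algorithm". Block sizes vary, and no stratification factor is named.
- **Sample size (8.2).** "A sample size of N=20 per group will give 80% power to detect an effect size of 0.91". The test behind this figure is a t-test of the two arms, two-sided at the 5% level. Then: "Accounting for an estimated 20% attrition rate, we plan to randomize a total of 20*2/0.8=50 patients in the study". The paragraph ends: "To preserve statistical power, the sample will not be balanced with regard to MAT and non-MAT participants".
- **Primary analysis (8.3).** "Analysis of covariance (ANCOVA) will be used to compare liraglutide versus placebo treatment groups controlling for baseline values of craving". A mixed model with baseline and post-treatment values both as outcomes, and a 2×2 ANOVA of treatment by pre/post for cue-elicited craving, are also named. The EMA model tests treatment by time and adjusts for sleep, stress, hunger, affect, and pain and discomfort. None of these contains MAT.
- **Where MAT does appear (8.3).** "Secondary analyses of self-reported craving measures will evaluate the role of MAT, specifically BUP/NA, in these results". Moderators are to be examined through interaction terms.

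**The concern.** Buprenorphine/naloxone is a co-treatment that could plausibly affect opioid craving, and planning a separate analysis of its role shows that the investigators think so too. In a trial of 40 to 50 people, an unstratified list can leave the arms with different MAT shares. The primary models then have no term to absorb the difference. Any part of the outcome variance that MAT explains also stays in the error term.

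The secondary analyses do not repair this. They leave the primary estimate and its standard error as they are. If adjustment is chosen only after an imbalance has been seen, the choice is open to dispute. Section 2.3 says that a trend towards efficacy, with safety shown, would support a multi-centre second phase, so a disputed contrast has a cost even in a pilot.

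**Working it through.** **1. The plan's own figure.** Inputs from 8.2: 20 per arm, standardised effect 0.91, two-sided 0.05. Noncentrality = 0.91 / √(1/20 + 1/20) = 0.91 / 0.316 = 2.878. The noncentral t with 38 df gives power 80.1%. Randomised: 40 / 0.8 = 50. Both figures reproduce.

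**2. Power with MAT balanced across arms and adjusted for.** Noncentrality = 0.91 / √[(1 − R²) × 0.1], 37 df, where R² is the share of outcome variance that MAT explains (assumed; the documents give no value).

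| R² | Noncentrality | Power |
|---|---|---|
| 0 | 2.878 | 80.0% |
| 5% | 2.952 | 82.0% |
| 10% | 3.033 | 84.0% |
| 20% | 3.217 | 88.0% |

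The worst case costs less than 0.1 point. Adding MAT to an ANCOVA that already contains baseline craving (37 to 36 df, arms balanced) also costs less than 0.1 point.

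**3. Power with adjustment but no stratification.** The variance of the treatment estimate is multiplied by 1/(1 − ρ²), with ρ² = (p₁ − p₂)² / [4m(1 − m)], where p₁ and p₂ are the MAT shares in the arms and m is their mean. Averaged over chance imbalance, power is 79.0% at R² = 0 (a loss of about 1.1 points), 81.0% at 5%, 83.0% at 10% and 87.1% at 20%. Break-even is at R² of about 2.8%.

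**4. Does the enrolled mix matter at fixed N?** With MAT in the model, the mix does not enter the residual variance. Without it, the outcome variance is s² + m(1 − m)D², where D is the MAT effect and s the residual SD. Moving from a 30:70 to a 50:50 mix raises m(1 − m) from 0.21 to 0.25. For D = 10, s = 25 the variance rises by a factor of 650/646 = 1.006; for D = 20, s = 20 by 500/484 = 1.033. That small penalty is what adjustment removes, so it argues for including MAT.

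**5. Chance imbalance.** Two independent binomial counts, probability that the MAT shares differ by at least 0.20:

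| Assumed MAT share | 25 per arm | 20 per arm |
|---|---|---|
| 30% or 70% | 16.4% | 22.6% |
| 40% | 19.3% | 25.8% |
| 50% | 20.3% | 26.8% |

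**6. Effect on the estimate.** Shift = imbalance × D. For D of 10 to 20 VAS points beyond what baseline craving captures (assumed), 0.20 × 10 = 2 and 0.20 × 20 = 4 points. With s of 20 to 25 (assumed), the standard error of the difference is s√0.1 = 6.3 to 7.9, so the shift is 2/7.9 = 0.25 to 4/6.3 = 0.63 of a standard error. At a 50% MAT share, the unadjusted variance is 1 + 0.25 × 100/625 = 1.04 to 1 + 0.25 × 400/400 = 1.25 times the adjusted variance.

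**7. Which term each model needs.** In the mixed model and the 2×2 ANOVA, the treatment effect is a difference in pre-to-post changes. A MAT main effect is constant within a person and cancels from each person's change. A simulation with 20 per arm and a 30-point MAT imbalance confirms this: the treatment-by-time estimate was −2.591 (SE 5.639) with and without the main effect. Only MAT-by-time changed it. The same reasoning applies to the EMA rate-of-decline contrast. In the ANCOVA, the outcome is the post-treatment value, so the MAT main effect is enough.

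**The case against.** **The 8.2 sentence is about something else.** A reader might infer that the plan cites power as its reason for leaving MAT out of the randomisation and the model. The documents do not support that. The sentence sits in the sample-size section and speaks of the sample, most naturally meaning no quota for the enrolled mix. No reason is given for omitting the covariate. What remains is that the sentence does not support the omission on either reading. A quota could cost power by slowing recruitment, but the plan does not argue this.

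**Chance imbalance is not bias.** It is already reflected in the standard error and does not raise the type I error rate. This stands. The gain is precision and a primary contrast that is harder to dispute.

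**Baseline craving may do the work already.** A MAT effect present on Day 1 is partly absorbed by the baseline covariate. This stands too: the 2-4 points apply only to an effect beyond baseline, and the power gains may be smaller than shown.

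**MAT is not ignored.** True, but an interaction test would have only about 20-29% power for an interaction of 0.91 SD (40 completers, assumed MAT share 20-50%), and it does not adjust the primary estimate.

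**MAT status can change after randomisation.** Patients are approached within 2-3 days of starting treatment (7.2.1), and a patient who begins buprenorphine/naloxone later is classed as non-MAT. This weakens the covariate, but a later status would be a post-randomisation variable and should not replace it.

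**Conclusion.** The point holds as a cheap improvement of low severity. MAT status is collected at enrolment, is plausibly prognostic, and is absent from both the allocation and every primary craving model. The 8.2 power sentence does not justify that absence.

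Two stronger readings should be avoided. Adjustment is nearly free, not free: without stratification it costs about 1 power point on average if MAT is not prognostic. Nor is a material imbalance likely: a difference of 20 points or more has a 16-27% chance over the ranges used, so most trials of this size would not see one.

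The MAT share, the MAT effect, the residual SD and the variance explained are all assumptions, because the documents give none of them. The omissions, the reproduced 80.1% and the sub-0.1-point cost of balanced adjustment do not depend on them. Severity stays low because 8.2 calls the study exploratory and its purpose the collection of pilot data.

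**What to change.** In 8.3:

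- Add MAT status at randomisation (yes/no, from the medication record) as a covariate in the primary ANCOVA.
- Add MAT and MAT-by-time to the mixed model, the 2×2 analysis and the EMA model. A main effect alone would leave the treatment-by-time contrast unchanged.
- State that MAT started after randomisation does not alter the covariate.
- Keep the planned secondary analyses of the role of MAT.

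In 8.2, delete the power rationale, or reword the sentence to say only that no quota is set for the enrolled mix.

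Optionally, generate the list in 7.4.3 separately by MAT status for participants not yet randomised.

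The cost is SAP wording and one degree of freedom in the ANCOVA (a further one for MAT-by-time in the repeated-measures models). Without stratification, about 1 power point is lost on average if MAT predicts nothing, with break-even at about 3% of variance explained. N stays at 50, with no new data collection and no change to patient care.
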